Data capture, verification, and disposition: Data will be primarily captured on paper records. Majority of the study instruments (such as Aberrant Behavior Checklist, Social Responsiveness Scale, Autism Diagnostic Observation Schedule, Vineland, Leiter scale) are provided as paper booklets and they will be used as the primary data capture devices. Additional information, such as physical examination findings, medical history records etc. will also be captured in paper records. After the study is complete, we will keep the study records for future regulatory purposes for a period of 7 years, at which time all study records will be destroyed. However the documents containing identifiable information will not be stored after the study ends; they will be destroyed after study is completed.

In addition, we will use a secure computer database to transfer the paper data records to an electronic format. University of Massachusetts Medical School has contracted the RedCap clinical trials software database solution. REDCap (Research Electronic Data Capture) is a secure web-based application built around HIPAA guidelines to support data capture for research studies. It allows users to build and manage online surveys and databases or a combination of both quickly. REDCap features automated export procedures for seamless data downloads to Excel, PDF, and common statistical packages (SPSS, SAS, Stata, R). Also included are a built-in project calendar, a scheduling module, ad hoc reporting tools, and advanced features, such as branching logic, file uploading, and calculated fields. The REDCap Software sits on a dedicated server behind a firewall to eliminate all nonessential access credentials. The data itself is isolated on a separate server that sits behind an additional firewall layer for added security. Interaction between REDCap and the client is encrypted via SSL. To ensure accuracy of transfer of data from paper to electronic format and to minimize data entry errors, all data that will be entered to RedCap will be double entered by two independent study staff members. After the study is complete and all data has been collected and entered into the database, the database will be locked out from any further editing.

Storage of laboratory samples: The following storage specifications will be met:

- a. For safety evaluations: The blood tubes/vacutainers will be labeled with study participant's unique ID number and shipped right away to the UMass Clinical Research Center's lab for analysis.
- b. For biomarker evaluations: The vacutainer will be labeled with the ID number, and the blood processed within 2 hours of collection for isolation of monocytes. The monocytes so isolated will be labeled with the unique study ID number and frozen in an appropriate culture media at -80C for a period not exceeding 3 months in the -80 freezer at UMass Memorial's Clinical Research Center. These samples will then be shipped to Johns Hopkins University (Lewis B. and Dorothy Cullman Cancer Chemoprotection Center, and Department of Pharmacology and Molecular Sciences, The Johns Hopkins University School of Medicine, Baltimore, MD 21205) for analysis of biomarkers (details below). The tube containing urine will be labeled with the ID number and stored at -80C until shipment.

Shipping of laboratory samples and laboratories performing evaluations:

- a. For safety evaluations: The samples will be tested at University of Massachusetts Memorial Medical Center Clinical Trials Unit Clinical Research Laboratory (located at Clinical Trials Unit, UMass Memorial Ambulatory Care Center, 1st Floor, [name]).
- b. For biomarker evaluation: These evaluations will be conducted at Lewis B. and Dorothy Cullman Cancer Chemoprotection Center, and Department of Pharmacology and Molecular Sciences, The Johns Hopkins University School of Medicine, Baltimore, MD 21205.
- c. Transportation of samples: The blood and urine samples for biomarker evaluation will be transported frozen. To ensure that proper temperature is maintained during transport they will be shipped in special Styrofoam containers in dry ice. The

person arranging specimen packing and shipment will be trained in shipping and transportation of hazardous materials.

13) Provisions to Monitor the Data to Ensure the Safety of Subjects*

Risk management and emergency response: Risks to subjects will be minimized by close follow-up and consideration of all reported symptoms and concerns of parents, guardians and caregivers. Regular examinations and laboratory testing of blood counts and serum chemistries, including liver function tests, renal function tests, and thyroid function tests will be performed at the screening visit, 7 week, 15 week, 22 week, 30 week and 36 week visits, and reviewed by the study team and Data Safety Monitoring Board. The PI or physician colleague will be on call 24/7 for any concerns of adverse events during the study. Risks of phlebotomy will be reduced by behavioral preparation, use of topical anesthetic and carried out by phlebotomists experienced in working with persons with autism. Protection of subjects will include confidential treatment of all health related information, and all research data will be coded, the reference codes to be maintained under lock and key by the PI and study coordinator at all times.

If lab signs of toxicity are found (AST/ALT > 2x upper limit of normal; serum creatinine > 1.2 mg/dl; TSH outside normal limits), the patient will discontinue study medication for 2 weeks before resuming the study medication, once lab values return to within study's acceptable limits. At the end of 2 weeks, we will do lab tests again. If at that time, lab tests are still not within study's acceptable limits (AST/ALT > 2x upper limit of normal; serum creatinine > 1.2 mg/dl; TSH outside normal limits), subjects will discontinue permanently the study medication (though they will still continue to be followed-up in the study). Lab tests are required at screening, 7-week, 15-week, 22 week, 30 week and closeout visits: Hematology and complete metabolic profile (including liver, kidney, thyroid function tests); urinalysis for protein and hemoglobin. Possible clinical side effects of sulforaphane will be monitored, including: GI disturbances (flatulence, soft stool, and large bowel movement), and frequent urination⁶³. Staff members will be available 24/7 for emergencies. Maximum amount of blood drawn at any stage during this study will not exceed 2 ml/kg body weight; also we will not exceed the minimal risk requirements of 3ml/kg in an 8 week period.

If any child in the study has a seizure while taking the medication, the study drug will be discontinued and study physicians and Data Safety Monitoring Board (DSMB) will be notified. The child will be evaluated by [name] or his designee, pediatrician or family doctor, and treated and followed up appropriately for the duration of the study. We will ask the parents to return with the child for repeat safety lab studies and to return unused study drug.

In the event of significant shifts in behavior, based on the family's experience and judgment, the child will be examined by the study physician(s) or the child's pediatrician, the study drug will be temporarily discontinued for 2 weeks and DSMB notified. If the behavior(s) subside, the medication will be resumed on the previous schedule. Since

children with ASD often have cyclic behavior changes without respect to the medications they are taking, we will rely primarily on the caregivers' experience in assessing whether the behavior(s) in question are out of the norm for their child. However, we will be cautious in evaluating the child for possible medical reasons for the change in behavior (e.g., gastrointestinal discomfort, disordered sleep). If adverse behaviors do not subside after 2 weeks and no medical cause for the behaviors is found, the study medication may be restarted if the DSMB, study physicians and the parents agree. Otherwise, medication will not be restarted and we will ask that the family return the remaining study drug supply.

We will constitute study drug pause and study drug stop rules based on objectively measurable criteria. These criteria appear below:

Subject Drug Pause Criteria: Subjects will be asked to stop taking study medication for 2 weeks if:

1. At 7 week visit, subjects reported any serious side effects and subsequent laboratory tests are outside of study's acceptable limits - liver function tests (AST/ALT > 2x upper limit of normal); renal function tests (serum creatinine > 1.2 mg/dl); thyroid function tests (TSH outside normal limits).
2. At 15 week visit, subjects reported any serious side effects and subsequent laboratory tests are outside of study's acceptable limits - liver function tests (AST/ALT > 2x upper limit of normal); renal function tests (serum creatinine > 1.2 mg/dl); thyroid function tests (TSH outside normal limits).
3. At any time during the study, subjects reported any serious side effects and subsequent laboratory tests are outside of study's acceptable limits - liver function tests (AST/ALT > 2x upper limit of normal); renal function tests (serum creatinine > 1.2 mg/dl); thyroid function tests (TSH outside normal limits).
4. There is a potential interaction of study medication with another medication a subject is taking. We will ask the subject to temporarily stop taking study medication if the other drug is a short term medication (e.g., a course of antibiotics, or prednisone).
5. Intercurrent illness (e.g., infection, asthma, accident or serious injury), requiring medical attention (e.g., emergency room visit or hospital admission). All such incidents will be reviewed with study physicians and the DSMB as they arise, and we will consult with the child's physician regarding the advisability of pausing the study drug and continuing follow up of the child's illness.
6. In the event of significant shifts in behavior, based on the family's experience and judgment, the child will be examined by the study physician(s) or the child's pediatrician, the study drug will be temporarily discontinued for 2 weeks and DSMB notified. If the behavior(s) subside, the medication will be resumed on the previous schedule. Since children with ASD often have cyclic behavior changes without respect to the medications they are taking, we will rely primarily on the caregivers' experience in assessing whether the behavior(s) in question are out of the norm for their child. However, we will be cautious in evaluating the child for possible medical reasons for the change in behavior (e.g., gastrointestinal discomfort, disordered sleep). If adverse behaviors do not subside after 2 weeks and no medical cause for the behaviors is found, the study medication may be restarted if the DSMB, study

physicians and the parents agree. Otherwise, medication will not be restarted and we will ask that the family return the remaining study drug supply.

Subject Drug Stop Criteria: At the end of 2 weeks, we will do lab tests again. At that time, subjects will discontinue the study medication permanently if:

1. Subsequent laboratory tests repeated after 2 weeks are outside of study's acceptable limits - liver function tests (AST/ALT > 2x upper limit of normal); renal function (serum creatinine > 1.2 mg/dl); thyroid function (TSH outside normal limits).
2. At any point of the study, extreme exacerbation of behavioral symptoms is noted, as above and these behaviors do not subside after 2 weeks of study drug stoppage and no medical cause for the change in behavior is apparent (e.g., gastrointestinal discomfort, disordered sleep).
3. If any child in the study has a seizure while taking the medication, the study drug will be discontinued and study physicians and Data Safety Monitoring Board (DSMB) will be notified. The child will be evaluated by [name] or his designee, pediatrician or family doctor, and treated and followed up appropriately for the duration of the study. We will ask the parents to return with the child for repeat safety lab studies and to return unused study drug.
4. At any time, if there is an interaction of study medication with another long term medication a subject is taking: In a case in which the other drug is the one which a subject is likely to require for a long period of time, subjects will discontinue study medication permanently if there is a possibility of adverse effects as a result of an interaction with that drug (for example, appearance of extrapyramidal signs in a subject taking risperidone).

Data Safety Monitoring Board: An independent data safety management board of 3 persons will be constituted to evaluate the continued safety of sulforaphane. This DSMB will consist of one pediatrician (from the department of Pediatrics at UMass Medical School), one child psychiatrist (from the department of Psychiatry at UMass Medical School) and one bio-statistician (from the department of Quantitative Sciences at UMass Medical School). This DSMB will meet twice a year and review all safety information collected in the past 6 months.

14) **Withdrawal of Subjects***

See study drug pause and stop criteria above.

15) **Risks to Subjects***

Sulforaphane Safety:

Cruciferous vegetables, including broccoli sprouts, are generally regarded as safe and are regular dietary components in many regions of the world. Previous estimates of the daily dietary intake of cruciferous vegetables vary regionally, averaging 40 g/day in Singapore⁶⁴, 11 g/day in the United States⁶⁵, 16 g/day in Canada⁶⁶, 30 g/day in the UK⁶⁷, and 112 g/day in Japan⁶⁸. There have been numerous adult human and animal studies

assessing the safety of sulforaphane. These studies are summarized in the safety and efficacy section of the Investigator Brochure.

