2. **Ohio Autism Clinical Impressions Scale – Improvement (OACIS-I)^{27,28}** is a 7 point, 10 domain scale that requires the clinician to assess how much the patient's ASD has improved or worsened relative to a baseline state at the beginning of the intervention and rated as: “1”, very much improved; “2”, much improved; “3”, minimally improved; “4”, no change; “5”, minimally worse; “6”, much worse; or “7”, very much worse. The 10 domains in which improvement is assessed are the same as those used in the OACIS-S scale. For this study, the proportion of patients who were rated as improved or very much improved on each of 10 domains of OACIS-I were compared between sulforaphane and placebo groups. This scale will be used to gauge the clinician assessment of improvement in autistic symptomatology at all follow up visits as compared to the previous study visits.
 3. **Social Responsiveness Scale (SRS)²⁶**: SRS is a parent- and/or teacher-reported 65 point scale covering 5 treatment subscales focusing on the social communication domain of ASD as observed in natural (non-clinical) settings. Each item on the scale inquires about an observed aspect of reciprocal social behavior that is rated on the questionnaire on a scale from “1” (never true), “2” (sometimes true), “3” (often true), and “4” (almost always true). Its quasi-interval, ordinal design facilitates assessing degrees of change and/or severity of symptoms in response to an intervention. The SRS scale scores is subdivided into 5 subscales (social awareness, social cognition, social communication, social motivation and autistic mannerisms). This scale will be used at all study visits and the scores (as well as change thereof from the baseline visit) will be used as one of the clinical outcome measures assessing social interaction skills in the study.

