Pilot Study to Determine Biomarkers: Prior to the main clinical trial, we will carry out a pilot study in 10 children with ASD, 6-12 years of age, who will receive sulforaphane, 2.2 micromoles/kg daily for 14 days. We will collect blood and urine samples before and at the end of treatment, in order to measure several parameters that are likely to demonstrate expected effects of sulforaphane, to standardize the assays and procedures, and to determine the most effective measures. Further details of the pilot study are discussed below.*

Study Design (Specific Aim 1): Following the pilot study for biomarkers, we will conduct a randomized, double-blind, placebo-controlled phase-2 clinical trial of sulforaphane in a single-arm crossover design in 3 phases, in 50 boys and girls (ages 3-12 years) with moderate to severe ASD (see Figure 1 below). In Phase 1 we shall treat participants for 15 weeks (50% with sulforaphane ((2.2 micromoles/kg body weight)), 50% with placebo of identical appearance). In Phase 2, all children will receive sulforaphane (2.2 micromoles/kg b.w.) on open label for an additional 15 weeks. In Phase 3 (6 weeks), participants will receive no sulforaphane, then return for followup at the end of the study. We project that treatment with sulforaphane will be associated with statistically significant improvements in physicians' global impressions, aberrant behaviors, social responsiveness and adaptive behaviors (see descriptions of outcome measures and statistical plan below).

Study variables will include clinician and parent assessments, and both clinical and scientific laboratory test measurements to evaluate for signs of toxicity and potential biomarkers of sulforaphane's effects. Our primary outcome measure will be the Ohio Autism Clinical Global Impression Scale (OACIS)^{27,28}. Secondary outcome measures will include the Aberrant Behavior Checklist (ABC)²⁵, Social Responsiveness Scale (SRS)²⁶, and Vineland Adaptive Behavior Scale (VABS)³⁰. The OACIS will be completed at each of 5 visits by clinicians; the ABC, SRS and VABS will be completed by the parents. All participants will have moderate to severe ASD, according to ADOS criteria as part of the screening process. Control subjects will be those children who

receive placebo for 15 weeks during Phase 1. All children will receive active sulforaphane during Phase 2.

[figure not shown]

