1. **Screening/baseline visit (double blind Phase 1):** This visit will take around 2.5 hours to complete. All participants will undergo a pre-screen assessment to determine if basic eligibility criteria are met. Qualified study staff will ask questions related to the above described inclusion/exclusion criteria. The pre-screen may be completed by telephone or direct interview. Some subjects may require a more extensive examination to ensure that their autism meets the study's inclusion criteria. An informed consent will then be obtained. Autism diagnosis will be confirmed clinical judgment corroborated by administration of the Autism Diagnostic Observational Scale (ADOS)²⁹. Those who have had an ADOS administered by an accredited professional within 3 years of study enrollment will not need to repeat this assessment if documentation of results can be provided. In that case, we will reconfirm diagnosis with a clinician check-list at enrollment (DSM-V checklist of symptoms). A Leiter-3 assessment will also be performed as a measure of nonverbal IQ³¹.

A complete, baseline history, physical and neurological exam will be performed. OACIS-S^{27,28}, SRS²⁶, ABC²⁵ and Vineland Adaptive Behavior Scale³⁰ will also be performed to quantify disease severity. Also, clinical laboratory tests (CBC and platelets, complete metabolic profile, including liver and renal function tests and thyroid stimulating hormone), blood for research laboratory tests (Nrf2, heat shock proteins, measures of oxidative stress and mTOR) and a urine sample for urinalysis will be obtained. The maximum amount of blood to be drawn at any stage during this study will not exceed 2 ml/kg body weight; we will also not exceed the minimal risk limitation of 3 ml/kg in an 8 week period.

If the blood tests done at the time of screening visit (liver function tests, renal function tests and thyroid function tests) are within study's acceptable limits (AST/ALT < 2x upper limit of normal, serum creatinine < 1.2 mg/dl, TSH within normal limits), we will either mail the study drug to study participants or ask their parents/guardians to pick up the study drug. The subject will be enrolled after he and/or his legal guardian agree to a comprehensive informed consent.

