At this visit, the study participant/s will already have been randomly assigned to either the sulforaphane or placebo group in the ratio of 1:1 by the study statistician. As mentioned above, after the safety labs come back normal, we will mail the study participants (or ask their parents to pick up) an 8 week supply of study medication (sulforaphane or placebo) that will last until the 7 week visit, plus a one week buffer. We will provide detailed instructions to subjects/parents/guardians on how to take the medication and include these instructions along with the medication package, and they will be made aware (and given written instructions) on how to recognize any side effects associated with the medication. They will be asked to call the study staff in case they have any questions or concerns.

2. **7 week visit (double blind Phase 1):** Enrolled subjects will then be asked to come for their 7 week (follow-up) study visit, where OACIS-I, SRS, ABC and Vineland Adaptive Behavior Scale will be administered. A complete physical examination will be performed and vital signs obtained. This visit will take ~ 1.5 hours to complete. They will be asked about any serious side effects they might have experienced. Also, clinical laboratory tests (CBC and platelets, complete metabolic profile (including liver function tests, renal function tests, thyroid function tests) and research laboratory tests blood - (Nrf2, heat shock proteins, measures of oxidative stress and mTOR) and urine (isoprostanes) will be obtained. Maximum amount of blood drawn at any stage during this study will not exceed 2 ml/kg body weight; we will also not exceed the minimal risk limitation of 3 ml/kg in an 8 week period.

At this visit, we will give the study participants a further 7 week supply of study medication (sulforaphane or placebo) that will last until the next visit (15 week visit). Study participants will be asked to finish the medication from the previous lot before starting the latter batch. They will be asked to continue to take the study medication unless instructed otherwise. We will provide detailed instructions for subjects/parents/guardians on how to take the study medication along with the medication package, and they will be made aware (and given written instructions) on how to recognize any side effects associated with the study medication. They will be asked to call the study staff in case they have any questions or concerns.

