Visit	Informed consent, eligibility criteria (ADOS, Leiter-3)	Adverse event reporting	Medical history, vitals, physical exam	Autism symptom severity (OACIS-S, OACIS-I, ABC, SRS, Vineland Adaptive Behavior Scale)	Blood draw (LFTs, RFTs, TSH, CBC, HSP, mTor, Nerf), urine sample for isoprostanes	Study drug dispensing	Visit duration
Double blind phase (50% participants receive sulforaphane and 50% receive placebo)							
Screening/ baseline visit	X		X	X	X	8 weeks	~ 2.5 hours
3 week phone survey		X					~ 15 minutes

7 week visit		X	X	X	X	7 weeks	~ 1.5 hours
15 week visit		X	X	X	X	8 weeks	~ 1.5 hours
Open label phase (all participants receive sulforaphane)							
18 week phone survey		X					~ 15 minutes
22 week visit		X	X	X	X	7 weeks	~ 1.5 hours
30 week visit		X	X	X	X		~ 1.5 hours
36 week visit		X	X	X	X		~ 45 minutes

11) Data and Specimen Banking*

We plan to store leftover blood and urine samples in -80 C freezer in the Dept. of Pediatrics at UMass and the Cullman Chemoprotection Laboratory at Johns Hopkins for a period of 3 years after completion of the study. They will be accessed by the P.I. or study staff. The samples will continue to be de-identified and labeled with unique study I.D. numbers. The link between the study ID and identifiable information will only be accessible by the UMass personnel. At the end of 3 years the samples will be forever anonymized, and the link between study ID and identifiable information will be destroyed. We will make application to the IRB for any further studies to be conducted, by ourselves or others, using these specimens.

12) Data Management*

Statistical Analysis: The OACIS-I, SRS and ABC data will be analyzed in a mixed model ANOVA with fixed effects for visit, treatment group, and their interaction and random participant-specific intercepts. The effect of sulforaphane on mean change in OACIS-I, SRS and ABC total scores from baseline will be estimated using linear contrasts. Estimates will be unbiased if any loss to follow-up is missing at random, conditional on the observed data and our model assumptions. Significantly greater improvement from baseline in mean scores among participants randomized to sulforaphane based on a two-tailed test at $\alpha = 0.05$ will be taken as support of our primary hypothesis.

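### OACIS-I, the sole primary scale, is given two reference points, and its analysis uses a week-0 value that the document's sections disagree on collecting

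*Combined protocol and SAP*

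**What the plan says.** **Reference point.** The OACIS-I entry in section 9 describes a rating of how far the child "has improved or worsened relative to a baseline state at the beginning of the intervention", on a 1 to 7 scale where 4 is no change and 2 is much improved. The entry closes by saying that in this study the scale will gauge "improvement in autistic symptomatology at all follow up visits as compared to the previous study visits". Section 12, Statistical Analysis, bases its decision rule on "Significantly greater improvement from baseline in mean scores among participants randomized to sulforaphane".

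**Week 0, analysis.** Section 12 fits a mixed model with visit, treatment, their interaction and a random participant intercept, and states: "The effect of sulforaphane on mean change in OACIS-I, SRS and ABC total scores from baseline will be estimated using linear contrasts". The power section assumes OACIS-I at 0, 7 and 15 weeks.

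**Week 0, collection.** In section 10 the screening/baseline visit names the severity form: "A complete, baseline history, physical and neurological exam will be performed. OACIS-S", followed by SRS, ABC and Vineland. Screening Procedures in section 24 also name only the severity form. The improvement form first appears at the "7 week (follow-up) study visit, where OACIS-I, SRS, ABC and Vineland Adaptive Behavior Scale will be administered". Study Design in section 10 says "The OACIS will be completed at each of 5 visits by clinicians", which matches the five follow-up visits. On the other side, the schedule table closing section 10 has a single column, "Autism symptom severity (OACIS-S, OACIS-I, ABC, SRS, Vineland Adaptive Behavior Scale"), ticked at screening/baseline, and the section 10 text on follow-up says OACIS is obtained at every visit without naming the form.

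**Endpoint.** Section 9 lists the primary endpoint as the OACIS-I average score, and ABC and SRS as changes from baseline. The power section keeps that split: a 15-week score difference for OACIS-I, changes for ABC and SRS.

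**The concern.** OACIS-I supplies the only primary endpoint and two secondary response rates. The two sentences in section 9 give different week-15 scores for any child who changes before week 7. The visit narratives do not settle the matter, because they administer the scale without restating its reference. Under a preceding-visit reading, the week-15 score counts only change since week 7. Benefit already reached and held disappears from the primary comparison and from the week-15 response rates on which the power statements rest. A rating made against the wrong reference may not be recoverable later.

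The week-0 problem is different in kind. An improvement rating made before treatment has nothing to measure, so a change from week 0 is either not computable or a change from a constant. If the plan leaves this open, the analyst decides how to handle week 0 in the primary test.

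**Working it through.** **1. One child, two references.** A child is much improved by week 7 and stable afterwards.

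| Reference | Week 7 | Week 15 |
|---|---|---|
| Start of intervention | 2 | 2 |
| Immediately preceding visit | 2 | 4 |

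**2. Response endpoints.** Inputs from Power Calculations: 54% v 9% (aberrant behavior), 46% v 7% (social communication), 22 per arm, two-sided 0.05. I used exact Fisher power. The plan's figures come back first: 88% (plan 88%) and 81% (plan 82%).

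Now assume the preceding-visit reading, and that a share f of responders arrive by week 7 and hold. The sulforaphane rate at week 15 becomes (1 - f) times the plan rate. For f = 0.25, 54% x 0.75 = 40.5% and 46% x 0.75 = 34.5%. For f = 0.5, the rates are 27% and 23%. The lower power in each range keeps the placebo rate; the higher multiplies it by (1 - f) too.

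| Endpoint | n per arm | Plan rates | f = 0.25 | f = 0.5 |
|---|---|---|---|---|
| Aberrant behavior | 22 | 88% | 60-70% | 24-44% |
| Aberrant behavior | 25 | 92% | 65-75% | 26-47% |
| Social communication | 22 | 81% | 53-62% | 21-36% |
| Social communication | 25 | 85% | 58-68% | 22-36% |

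The documents give no value for f.

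**3. Primary score.** Plan inputs: difference 4, SD 4.9, 20 per arm, 80% power. A two-sample t-test gives 71%, and 81% at the planned 25 per arm. The inputs also do not fit an average of 1-7 items. Such a score with mean m has variance at most (m - 1)(7 - m). Arm means m and m + 4 allow the largest common variance at m = 2, where (2 - 1)(7 - 2) = 5 and (6 - 1)(7 - 6) = 5, so SD is at most 2.24.

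- With SD 2.24, 25 per arm and half the effect lost (difference 2), power is still 87%.
- If the score were instead a sum over domains and the plan's inputs stood, power at 25 per arm would fall from 81% to 56% (difference 3) or 29% (difference 2).

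That spread is why no reliable figure can be given.

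**4. Constant week 0 in the random-intercept model.** Let weeks 7 and 15 have variance 1 and correlation r, with week 0 fixed. The constant cancels between arms, so with complete data the contrast equals the week-15 difference in means and the estimate is unchanged. The expected within-participant mean square is

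(1/2) x [2 - (2 + 2r)/3] = (2 - r)/3.

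The model gives week 15 minus week 0 a variance of 2(2 - r)/3 per child; the true variance is 1. Hence model SE / true SE = sqrt(2(2 - r)/3). Type I error comes from 40,000 simulated null trials per row, 25 per arm.

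| r (assumed) | SE ratio | Type I error |
|---|---|---|
| 0.3 | 1.06 | about 4% |
| 0.5 | 1.00 | about 5% |
| 0.7 | 0.93 | about 7% |
| 0.9 | 0.86 | about 9% |

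With weeks 7 and 15 only and the week-15 difference as contrast, type I error was 4.8% throughout the range 0.3 to 0.9.

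**The case against.** The best defence is that the intended design can be recovered from the text. The scale definition and the decision rule in section 12 both point to baseline, and the plural in the disputed sentence can include the baseline visit. The primary endpoint in section 9 and the power section already treat OACIS-I as a score compared at 15 weeks, so the change-from-baseline sentence in section 12 may only be shorthand covering three scales. All of this stands. It shows which way to correct the text; it does not remove a contrary statement about how the primary scale will be used.

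Three further inferences are tempting, and the documents do not support them.

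- A reader might infer that OACIS-I is nowhere collected at week 0. The schedule table ticks a column that includes it, and section 10 elsewhere promises OACIS at each visit. The documents conflict; they are not silent.
- A reader might infer that an early responder drops out of the Fisher responder analysis. Section 12 ties the ABC and SRS criteria to 15 weeks but sets no week for OACIS-I, so a week-7 responder might still count. The loss applies to the week-15 rates used for power.
- A reader might infer an inflated false-positive rate. The preceding-visit reading would hide early benefit, not create false positives. The constant week-0 value is stated nowhere; even if entered, it is conservative at r = 0.3 and about nominal at 0.5.

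**Conclusion.** The point holds as an inconsistency that should be fixed. It does not show that the trial will rate or analyse the primary endpoint wrongly. Two things are established from the text alone: section 9 gives the primary scale two reference points, and section 12 uses a week-0 OACIS-I on which the collection sections disagree and which could carry no information.

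The sizes are conditional. The power losses for the response endpoints need both the preceding-visit reading and an early-response share that the documents do not give. For the primary score no reliable loss can be stated, because the plan's difference and SD do not fit a 1-7 average; that is a separate matter. The type I error range of about 4% to 9% needs a constant 4 entered at week 0 and week 7-15 correlations of 0.3 to 0.9, all assumed.

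**What to change.** 1. **Section 9, OACIS-I entry:** replace the closing comparison with previous visits by a comparison with the baseline state at the start of the intervention. Instruct raters to use the recorded baseline OACIS-S as the reference.
2. **Section 12, Statistical Analysis:** analyse the OACIS-I score at weeks 7 and 15 with no week-0 record, and make the week-15 between-arm difference the primary contrast. This agrees with the endpoint list and the power section. Keep change from baseline for SRS and ABC.
3. **Section 12, Power Calculations:** give the OACIS-I assessments as weeks 7 and 15.
4. **Schedule table, section 10:** show that OACIS-I is not rated at baseline. Do not remove OACIS-S from the follow-up visits in the same edit. The table ticks it there and the visit narratives do not mention it; reconcile that separately.

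The cost is wording and one rater instruction. No visit or assessment is added, since OACIS-S is already rated at baseline.
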